6.1.2 Rationale for Study Design

The prospective observational design offers the opportunity to explore the use, effectiveness, and safety of faricimab in nAMD and DME in a real-world clinical setting and to collect desired information by defining uniform data collection methods.

Typically, for clinical trials, the outcome of BCVA is used to analyze the efficacy of intravitreal treatments (IVTs); however, BCVA is seldom measured in the routine clinical practice. VA and its change over time is considered a standard endpoint to measure effectiveness of these treatments in the real-world setting. Therefore, it has been chosen as the primary effectiveness endpoint of the FaReal study to explore faricimab approved in nAMD and DME in a long-term real-world setting with a broader patient population. In routine clinical practice, VA measurements will be done at distinct timepoints using different methods; thus, the date of each measurement will be recorded from all routine visits and, where applicable, analyzed as per the appropriate window period planned around these timepoints. The results will be documented as measured per local practice and will then be converted automatically in the electronic case report form (eCRF) to the approximate early treatment DR study (ETDRS) letter score for comparability.

Key secondary effectiveness objectives will evaluate the impact of retinal treatment patterns on VA in terms of treatment frequency, monitoring visit frequency, total visit frequency, and time interval between treatments. The observational study design will allow the required information on real-world retinal treatment patterns to be collected and explored to meet these objectives.

The study also includes a Safety Endpoint of evaluating the ocular and systemic safety/tolerability of faricimab approved in nAMD and DME. This study design allows the collection of all ocular and non-ocular AEs (serious and non-serious) to allow comprehensive data collection for this endpoint.

Regular interim analyses will be performed throughout the study duration to evaluate effectiveness and safety of faricimab. Additional details on these can be found in section Interim and Final Analyses and Timing of Analyses ([Section 6.7.5](#)).

6.1.3 **Number of Patients Observed in the Study**

This study aims to enroll a total of approximately 850 patients treated with faricimab (n=600 patients with nAMD and n=250 patients with DME), who will be contributing data for one or both eyes, to enable meaningful analysis of study cohorts, sub-cohorts and subgroups by baseline characteristics, and other factors. Sub-cohorts will include treatment naïve patients (approximately 240 nAMD and 100 DME patients) and patients previously treated with anti-VEGF (approximately 360 and 150 patients in the nAMD and DME cohorts, respectively).

Cohort	Total**	Sub-cohorts (by Treatment Status)		% Treatment Naïve*
		treatment naïve**	pre-treated**	
nAMD	600 (70%)	240 (70%)	360 (70%)	40%
DME	250 (30%)	100 (30%)	150 (30%)	40%
Overall	850 (100%)	340 (100%)	510 (100%)	40%

DME = diabetic macular edema, nAMD = neovascular age-related macular degeneration

*Row percentage

**Column percentage

Recruitment will be open until approximately 850 patients have been recruited. The recruitment period may be expanded at the Marketing Authorization Holder (MAH)'s discretion.

6.1.4 **Sites**

Approximately 65 sites in Europe and Israel, with commercial availability/reimbursement and access to the faricimab, will be included. Additional centers may be added or substituted as required.

6.2 POPULATION

The main patient population for this study, that is new users of faricimab (initiated treatment at enrollment or within 3 months prior to enrollment) in nAMD or DME in at least one eye, has been chosen to allow the capture of the baseline information as it will coincide around the time of study enrollment.

The study will recruit patients who are naïve to anti-VEGF intravitreal therapy in the study eye and those who have previously been treated with anti-VEGF intravitreal therapy in the study eye. Overall, study participation of patients previously treated with intravitreal anti-VEGF will be capped at a maximum of approximately 60% in each

indication. Expected proportion of nAMD and DME patients in the study population is 70% and 30%, respectively.

Patients must meet the following criteria for study entry:

1. Adult patients (≥ 18 years), who have provided signed informed consent, as required per local regulations.
2. Patients, as defined by local regulations and local faricimab product label, who are initiating treatment with faricimab at time of enrollment or have initiated treatment with faricimab within 3 months prior to patient enrollment, in DME or nAMD in at least one eye according to the investigator's discretion in routine clinical practice for anti-VEGF treatment naïve and pre-treated patients.
3. Patients have received at least one faricimab treatment (the first dose) in the study eye.

Patients who meet any of the following criteria will be excluded from study entry:

1. Concomitant participation of the patient in any investigational ophthalmology clinical trial that includes receipt of any ophthalmological investigational drug or procedure within the last 28 days prior to enrollment
2. Current participation in any interventional clinical study
3. Active ocular inflammation and/or suspected/active ocular infection in either eye
4. Patients in whom the study eye has been treated with faricimab for more than 3 months prior to enrollment
5. Patients treated with faricimab who have and are currently participating in patient support programs (PSP) that are Market Research and Patient Support Programs (MAP) including Post Trial Access Programs (PTAP) and Compassionate Use Programs (CUP)
6. Patients with non-ocular sight threatening disease which have an effect on primary endpoint (VA), e.g.: apoplexia
7. Hypersensitivity to the active substance or any of the excipients of Vabysmo (as per label)

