6 RESEARCH METHODS

6.1 STUDY DESIGN

6.1.1 Overview of Study Design

The FaReal study is a non-interventional, prospective, multinational, multicenter study designed to collect real-world data on patients treated with faricimab in nAMD and DME in the real-world routine clinical practice with primary prospective data collection (NIS PDC) and retrospective collection of prior medical/treatment history data from medical records.

Participation in this study will not change or influence a patient's standard of care in any way. The decision to start treatment with faricimab must be taken independently by the treating physician and before the decision to invite the patient into the study.

This study aims to enroll approximately 850 patients from approximately 65 sites (in 18 countries in region Europe and Israel). The expected duration of the study is approximately 4 years.

Adult patients fulfilling the eligibility criteria who sign informed consent (as required per local regulations) will be enrolled and followed up prospectively from enrollment until completion of 2 years of participation, death, withdrawal of consent, participation in an investigational ophthalmology clinical trial, early termination of the study, or discontinuation of the study site, whichever occurs first. Patients are free to withdraw participation at any time.

Retrospective data will be collected for pre-treated patients pertaining to their previous anti-VEGF treatments.

All patient visits will be conducted according to usual local clinical practice. No study-specific visits are mandated by the study protocol, no patient visits or remote consultations are mandated by the study protocol, and no additional tests will be performed on patients due to their participation in this study. Data will be collected only when patients present for their routine visits or are contacted remotely. Retrospective data from enrolled patients will be collected from the patient's medical history.

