Anonymized data will be shared with the medical and scientific community to foster research and support evidence generation. The data elements collected will address different types of research questions through registry-based studies such as secondary data use (SDU) studies.

Start Date of Study

Patient enrollment will be initiated at each site, upon approval from regulatory authorities and IRBs/ ECs, as per local regulation and site agreement implementation and approval of faricimab treatment in nAMD and/or DME according to local labeling. The study start date will be the date of the first patient enrolled.

Study Duration

The expected duration of the study is up to 4 years, depending on the enrollment period duration. This includes approximately 1 to 2 years of recruitment and 2 years for follow-up of every patient (unless the patient discontinues early from the study).

Faricimab—F. Hoffmann-La Roche Ltd

Protocol MR45586, Version 1.0

Baseline Date and Index Date

Baseline is defined as the date when a patient initiates treatment with faricimab in at least one eye (first eye in case of both eyes being treated).

Index date is defined as the date when treatment is initiated at the eye-level. If both eyes are treated with faricimab and the treatment start dates are different, each start date will be used as the index date for the respective eye.

Enrollment Date

Enrollment date is the date the patient signs the Informed Consent Form to participate in this study.

Enrollment date cannot occur earlier than index/baseline date.

End of Study

The study ends when all participants have either completed at least 2 years of follow-up or have ended their participation in the study due to death, withdrawal of consent, participation in an investigational ophthalmology clinical trial, early termination of the study, or discontinuation of the study site, whichever occurs first.

The end of the study date will be the date on which the last information pertaining to the last included patient is recorded in the database.

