6.7.2 Effectiveness Analyses

6.7.2.1 Primary Effectiveness Analyses

Primary effectiveness analyses will be performed per cohort and per sub-cohort, at the eye-level, for the EFAS-EL.

The primary effectiveness endpoint is the change in VA (approximate ETDRS letter score) from index date to month 12 per nAMD and DME and per treatment naïve and pre-treated sub-cohorts. VA will be measured as per the local practice at index date and at month 12. To allow statistical analysis of the different clinical methods used to measure VA, the assessments will be automatically converted to the approximate ETDRS letter score. The approximate ETDRS letter score conversion table can be found in [Appendix 3](#).

Both actual values at index date and month 12 and change from index date in VA (approximate ETDRS letter score) to month 12 will be summarized descriptively.

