Cumulative time spent in each treatment regimen (i.e., Fixed regimen, T&E, PRN, Other), per nAMD and DME, and per treatment naïve and pre-treated sub-cohorts will be summarized descriptively using mean, median, SD, first quartile, third quartile, minimum, and maximum.

The number and percentage of eyes obtaining treatment intervals of Q8W, Q12W, Q16W and other at 12 months and 24 months will be calculated and summarized by study cohort and for treatment naïve and pre-treated patients (by pre-treatment type).

The number and percentage of eyes discontinuing faricimab treatment in each cohort will be calculated at months 3, 6, 12, and 24 (the reason for treatment discontinuation will be reported at the same time periods).

The number and percentage of eyes switching treatment regimen or treatment type and reason for switch at months 3, 6, 12 and 24 will be calculated and summarized per nAMD and DME.

Time to first treatment switch will be calculated per nAMD and DME and summarized using Kaplan-Meier estimate.

Number and percentage of eyes switched from faricimab to a non-faricimab product will be calculated and summarized at index date, months 3, 6, 12 and 24.

Number, type and frequency of ocular concomitant and subsequent medications received during the study period will be calculated and summarized descriptively by eye.

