6.9 LIMITATIONS OF THE RESEARCH METHOD

The study might be limited by the factors described below:

- Data on effectiveness of non-Roche products will not be collected, which limits the ability to compare the effectiveness of faricimab with non-Roche products that are used in routine clinical practice.
- Although the study will enroll a large number of patients from multiple countries overall, the patients within each country will be enrolled from a few selected sites. This may limit the representativeness of the results to the underlying population within each country. Also, due to logistics barriers, consecutive enrollment is not mandated and the patients who choose or are invited to enroll in the study may differ from those who are not (e.g., relatively healthier individuals choose to enroll in the study); this will limit the representativeness of the results.
- The primary effectiveness endpoint of VA may be measured using different methods depending on the local clinical practice, leading to heterogeneity in the assessment methods. However, the change in VA will be analyzed by approximate ETDRS letter score for comparability and will be calculated for each eye. It is anticipated that measurements over time for the same eye at the same site will generally be conducted using a consistent method, thus limiting the impact of heterogeneity on the outcome.
- The flexible inclusion criteria, allowing inclusion of difficult-to-treat patients, and variable treatment schedules as well as treatment decisions based on respective clinical practice guidelines across countries and regions might result in variations in the study outcomes. Thus, the study may have a lower internal validity. However, such variety of data will help shed light on the critical factors that HCPs from different countries consider while making clinically important decisions for diverse patient populations in a real-world setting.
- The data to be captured for this study will be collected from the ophthalmologic sites, and not from any other healthcare providers. Information on non-ocular AEs may therefore not be recorded in the data at the ophthalmologic sites and may be underreported.

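### Patients may be selected up to 3 months after the first injection, when early VA and OCT may be known, so VA and CST change counted from index can be biased by an unmeasured amount

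*Protocol*

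**What the plan says.** - **Time zero.** Section 6.1.1: "Index date is defined as the date when treatment is initiated at the eye-level". Section 6.7.2.1: "The primary effectiveness endpoint is the change in VA (approximate ETDRS letter score) from index date to month 12". The secondary VA and CST changes run from the same date (Section 5.2.1).
- **Entry.** Inclusion criterion 2 in Section 6.2 covers patients starting at enrolment and those who "have initiated treatment with faricimab within 3 months prior to patient enrollment"; exclusion criterion 4 closes entry after 3 months. Section 6.1.1 adds: "Enrollment date cannot occur earlier than index/baseline date".
- **Invitation.** Section 6.1.1 requires the treatment decision to be made "before the decision to invite the patient into the study". Section 6.2.2 asks sites for enough naïve and pre-treated patients but does not say when to invite.
- **Disclosure.** Section 6.9 states that "consecutive enrollment is not mandated and the patients who choose or are invited to enroll in the study may differ from those who are not". Its example is that "relatively healthier individuals choose to enroll in the study", and the consequence it draws is limited representativeness.
- **Switching.** Section 6.7.2.2: "Time to first treatment switch will be calculated per nAMD and DME and summarized using Kaplan-Meier estimate".

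**The concern.** Follow-up for effectiveness starts at the first injection, but membership of the cohort can be settled up to 3 months later. Appendix 5 describes an initiation phase of 4 monthly doses, which at months 0, 1, 2 and 3 fits inside that window. A patient approached late in the window may already have several VA and OCT results in the chart. The Effectiveness Analysis Set needs an index VA and one post-index VA (Section 6.7.1.2), and both can predate consent.

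If sites tend not to invite patients who are doing badly, or such patients tend to decline, selection acts on part of the outcome itself. That differs from enrolling healthier people in general: it shifts the mean change from index, and a larger sample does not reduce the shift. The month-3 result is the most exposed. Months 6 and 12 are affected to the extent that they correlate with early response.

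**Working it through.** **1. Yardstick from the protocol.** Section 6.7.6 defines precision as the full width of the 95% CI, with SD 12 or 14 and 5% drop-out. Width = 2 × 1.96 × SD / √(0.95n).

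| Sub-cohort | n | Width, SD 12 (stated) | Width, SD 14 (stated) |
|---|---|---|---|
| nAMD naïve | 240 | 3.12 (3) | 3.63 (3.6) |
| nAMD pre-treated | 360 | 2.54 (2.5) | 2.97 (3) |
| DME naïve | 100 | 4.83 (5) | 5.63 (5.6) |
| DME pre-treated | 150 | 3.94 (4) | 4.60 (4.6) |

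Table 3 is reproduced up to rounding. Halving the stated widths gives 1.25-1.8 letters for nAMD and 2.0-2.8 for DME.

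**2. Possible shift under selective entry.** The documents give no share of late enrolment and no link between response and invitation, so all of these inputs are assumptions:

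- month-3 change: mean 4, SD 10; month-12 change: SD 13; correlation ρ = 0.5 or 0.7
- share of candidates approached after early response is known: f = 0.3, 0.5 or 0.7
- relative probability of entry if the month-3 change is negative: r = 0.5 or 0.7

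The probability of a negative change is p = Φ(−0.4) = 0.345. The partial mean below zero is 4 × 0.345 − 10 × φ(0.4) = −2.30.

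- Mean among late entrants = (4 + (1−r) × 2.30) / (1 − (1−r) × 0.345). For r = 0.5 this is 6.22, a shift of 2.22. For r = 0.7 it is 5.23, a shift of 1.23.
- Late share among those enrolled: s = f·k / (f·k + 1 − f), with k = 1 − (1−r) × 0.345.
- Month-3 bias = s × shift. Month-12 bias = month-3 bias × ρ × 13/10.

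| r | f | s | Month 3 | Month 12, ρ = 0.5 | Month 12, ρ = 0.7 |
|---|---|---|---|---|---|
| 0.7 | 0.3 | 0.28 | 0.34 | 0.22 | 0.31 |
| 0.7 | 0.5 | 0.47 | 0.58 | 0.38 | 0.53 |
| 0.7 | 0.7 | 0.68 | 0.83 | 0.54 | 0.76 |
| 0.5 | 0.3 | 0.26 | 0.58 | 0.38 | 0.53 |
| 0.5 | 0.5 | 0.45 | 1.01 | 0.65 | 0.92 |
| 0.5 | 0.7 | 0.66 | 1.47 | 0.95 | 1.33 |

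Of the 12 month-12 values, 11 lie below the smallest half-width (1.25). Only the corner value of 1.33 exceeds it, and none reaches the DME half-widths.

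**3. Dependence on the selection rule.** Suppose instead that the worst share q of late candidates never enters, with SD 12-14 at both times. The month-3 shift is then f × SD × φ(z_q)/(1−q), where f is now the late share among those enrolled, and the month-12 shift is ρ times that.

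- f = 0.25, q = 0.05: 0.3-0.4 letters at month 3 and 0.2-0.3 at month 12
- f = 0.5, q = 0.1: 1.2-1.4 and 0.6-1.0
- f = 0.5, q = 0.2: 2.1-2.5 and 1.0-1.7

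The answer is driven by the assumed rule, which is why recording the entry delay is worth more than any assumed figure.

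**4. Timing.** Both models let selection act on the full month-3 change. Entry closes at 3 months, so that value is known only near the end of the window, or up to 30 days sooner if the ±30-day window given as an example in Section 6.1.1 applies. A patient enrolled at week 4 or 8 shows only a partial response. For a given strength of selection, the figures are therefore on the high side.

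**The case against.** The strongest reply is that Section 6.9 already discloses selective entry by both site and patient, with better health offered only as an example. The study is also descriptive, with no hypothesis test, and an analysis by enrolment timing could sit in the SAP, which is not available here. All of that is fair. It reduces the gap in Section 6.9 to one unnamed mechanism and its consequence. It does not cover the instruction on when to invite, which is protocol content and cannot be repaired by an analysis plan once patients are enrolled.

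A reader might infer more than the documents support:

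- **That the results are biased upward.** No passage gives the late share, a link between response and invitation, or a direction. Upward is the plausible direction, not an established one.
- **That no analysis will reveal it.** Sections 6.1.1 and 6.7.4.4 leave further subgroups to the SAP.
- **That the switch curve counts time before enrolment as at risk.** Section 6.7.2.2 states no time origin or entry rule for that curve. A switch before consent does not bar entry, since Section 6.2 requires only one injection and Section 6.5.2 keeps patients who switch. Such switches can be recorded, and starting each eye's risk time at enrolment would discard them.
- **That the early-enrolled eyes should supply the reported month-3 result.** That would replace a planned all-eye result with a much smaller set.

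**Conclusion.** The point holds as a design weakness that is cheap to reduce. The protocol allows selection after early response is known, counts VA and CST change from before that selection, and does not name the mechanism. The resulting bias is possible, not shown. Under the assumptions in step 2 it is about 0.3-1.5 letters at month 3 and 0.2-1.3 at month 12, mostly below the nAMD half-widths and always below the DME ones. It could be negligible if most patients enrol at the index visit, as Section 6.2.1 suggests when it says eligibility focuses on eyes starting treatment at enrolment. It could be larger if poor responders are excluded outright. The all-eye results remain usable, but they need a companion result that selection on early response cannot have affected.

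**What to change.** - **Section 6.2.2:** ask sites to invite eligible patients at the first-injection visit wherever possible. This fits the rules that the treatment decision comes first and that enrolment is not earlier than index.
- **Section 6.7.2:** keep the all-eye VA and CST results as planned. Add a supportive analysis in eyes whose patient enrolled before that eye's first post-index VA. Tabulate days from index to enrolment by cohort and sub-cohort.
- **Switch and discontinuation:** show the same early-enrolled subset as a sensitivity analysis. Do not require delayed entry.
- **Section 6.9:** state that early response may be known at invitation or consent, and that this can bias change from index as well as limit representativeness.

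The cost is one sentence to sites and some analysis wording; both dates are already defined in the protocol. No eligibility or treatment rule changes. The price is precision. If 30-70% of enrolled patients are late, naïve DME falls from 100 to 70-30 patients, and the half-width 1.96 × SD / √(0.95n) rises to between 2.9 letters (n = 70, SD 12) and 5.1 (n = 30, SD 14). Pre-treated DME falls from 150 to 105-45. The subset is therefore supportive only. A difference from the all-eye result is not a clean estimate of the bias either, because sites that enrol early may differ in other ways.

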6.2.1 Rationale for Patient Population

This study aims to collect data from a broad real-world patient population treated with faricimab in nAMD and DME, as per clinical practice and labeling under EMA label or Food and Drug Administration (FDA) label (Israel) authorization and as per country label requirement. Therefore, minimal eligibility criteria will be applied to ensure a broad population.

As the primary objective of this study is to evaluate the effectiveness of faricimab for nAMD and DME on VA at 12 months after treatment initiation in the real-world setting, eligibility criteria focus on those patients' eye(s) that are initiating treatment at the time of enrollment. It is acknowledged that the effectiveness of faricimab may be different depending on whether an eye was previously treated with anti-VEGFs. Treatment naïve eyes are of particular scientific and medical interest as effectiveness and safety

outcomes will not be hindered by any long-term effects of previous treatments. Furthermore, a prospective follow-up of patients will enable a better recording of safety data, which is an important objective of this study.

Treatment naïve patients and pre-treated patients will be recruited in this study. Patients who had previously received intravitreal anti-VEGF treatment will be enrolled to assess the effectiveness of faricimab in switch patients and to incorporate the health economic aspects of previous treatments. The number of participants with prior intravitreal anti-VEGF therapy will be limited to 60% as the maximum proportion of the total and each indication enrolled.

The rationale for capping the number of pre-treated participants is based on the heterogeneous nature of this population with potentially a history of long-standing disease and irreversible retinal damage that may limit the possibility of detecting additional VA improvements.

